6.1.7 Device Specific Considerations

The device is comprised of multiple assemblies:

1. Chinrest Assembly

1.

- a. chinrest
- b. mount
- c. attachment to existing device
- 2. Forehead rest Assembly
 - a. forehead rest
 - b. attachment to existing device

While the shapes of the aforementioned assemblies are complex, their overall dimensions are in IPS unit system and have a tolerance of .01", unless stated otherwise, are as follows:

- a. 4.40" x 3.40" x 0.77"
 - b. 3.50" x 2.0" x 0.38"

CONFIDENTIAL

Version: 3.0

c. 5.67" x 1.22" x 1.65"

2.

- a. 5.0" x 2.10" x 0.61"
- b. 5.0" x 1.80" x 0.25"

Furthermore, the frequency of exposure will be for just one imaging session.

7 Study Procedures and Schedule

7.1 Study Procedures/Evaluations

7.1.1 Standard of Care Study Procedures

- · Medical history will be obtained from medical records
- Medication history should include medications currently being taken

7.2 Imaging Procedures

- Chin and forehead rest will be adjusted for each individual subject by following the appropriate procedure, shown in standard operating procedure attached
- OCT Imaging should include for each eye
 - o Acquisition of 1 image of the Macula
 - Acquisition of 1 image of the ONH
- Two separate questionnaires will be provided to the subject before and after being imaged

7.2.1 Clinical Laboratory Evaluations

Not applicable as no labs will be needs.

7.3 Concomitant Medications, Treatments, and Procedures

Not applicable.

8 Assessment of Safety

8.1 Safety, Adverse Events Risks and Discomforts

There is a risk of blurred vision and difficulty in near vision operation (e.g., reading and writing), which is common, due to the use of dilating drops. The effects of these drops will disappear within 3-4 hours after instillation. The participant may be asked to remain in the clinic in the event that they experience blurred vision and do not have an accompanying person.

Pupil dilation may cause an increase in eye pressure or the possibility of an angle-closure event, which happens in a rare configuration of the eyes. All subjects will be examined clinically Before dilating drops are instilled to identify eyes at risk, in which case no dilation drops will be used. If either of these risks should occur, the subject will be treated immediately with eye drops at no cost.

Ophthalmologic OCT imaging is performed in a non-contact fashion, so there is minimal risk of infection to the participant. To reduce the possibility of eye infection, all exposed surfaces near the eye, as well as the chin rest and forehead rest of the instrument, will be cleaned with alcohol before participants are examined. The risk of infection is low.

Version: 3.0

Imaging will be performed using commercial (FDA approved) and non-commercial (non-FDA approved) OCT imaging instruments. All devices are subject to standard medical regulatory and safety requirements and adhere to the American National Standards Institute safety standards for the use and exposure to lasers. There is no known cumulative risk for repeating OCT scans multiple times on the same day or on different days.

8.1.1 Adverse Event

The IRB and participants will be notified immediately of any new information, in regards to this study. Expected and serious adverse events that occur will be reported to the

IRB according to the IRB Reference Manual. Fatal or life-threatening adverse events with research intervention will be reported to the IRB within 24 hours of notice. If there is a major unresolved dispute between the research investigator and a research subject or between research investigators, a letter will be submitted to the IRB describing the dispute and identifying the parties involved.

All adverse events occurring during the study period will be recorded. At each contact with the participant, the investigator will seek information on adverse events by specific questioning and examination. Information on all adverse events will be recorded in the patient file immediately. The clinical course of each event will be followed until resolution, stabilization, or until it has been determined that participation in the study is not the cause. Serious adverse events that are still ongoing at the end of the study period will be followed to determine the final outcome.

A review of the outcome and adverse event data will be monitored by the PI and sub-investigators to determine whether the study should be continued, should be changed, or should be terminated. A copy of the DSMB report will be submitted to the IRB at the time of renewal.

The PI will be ultimately responsibility for the data safety monitoring of the overall study. ADSMB will include the PI, sub-investigators and clinical coordinators in conjunction with a licensed ophthalmologist, [name], who will meet once every two months to monitor cumulative data points such as patient questionnaire, data acquisition time, adverse events, serious adverse events, withdrawals, early terminations recruitment, retention, confidentiality and adherence to the study protocol. At the time of obtaining renewal approval from the IRB, a report indicating whether there is any change in the risk benefit considerations of the study will be submitted. There are no specific stopping rules for this study.

8.2 Time Period and Frequency for Event Assessment and Follow-Up

The occurrence of an AE or SAE may come to the attention of study personnel during study visits and interviews of a study participant presenting for medical care, or upon review by a study monitor. All AEs including local and systemic reactions not meeting the criteria for SAEs will be captured on the appropriate RF. Information to be collected includes event description, time of onset, clinician's assessment of severity, relationship to study product (assessed only by those with the training and authority to make a diagnosis), and time of resolution/stabilization of the event. All AEs occurring while on study must be documented appropriately regardless of relationship. All AEs will be followed to adequate resolution.

Any medical condition that is present at the time that the participant is screened will be considered as baseline and not reported as an AE. However, if the study participant's condition deteriorates at any time during the study, it will be recorded as an AE. UPs will be recorded in the data collection system throughout the study.

Changes in the severity of an AE will be documented to allow an assessment of the duration of the event at each level of severity to be performed. AEs characterized as intermittent require documentation of onset and duration of each episode.

Version: 3.0

The PI will record all reportable events with start dates occurring any time after informed consent is obtained until 7 (for non-serious AEs) or 30 days (for SAEs) after the last day of study participation. At each study visit, the investigator will inquire about the occurrence of AE/SAEs since the last visit. Events will be followed for outcome information until resolution or stabilization.

All unresolved adverse events should be followed by the investigator until the events are resolved, the subject is lost to follow-up, or the adverse event is otherwise explained. At the last scheduled visit, the investigator should instruct each subject to report any subsequent event(s) that the subject, or the subject's personal physician, believes might reasonably be related to participation in this study. The investigator should notify the IRB of any death or adverse event occurring at any time after a subject has discontinued or terminated study participation that may reasonably be related to this study. The IRB should also be notified if the investigator should become aware of the development of cancer or of a congenital anomaly in a subsequently conceived offspring of a subject that has participated in this study.

8.2.1 Unanticipated Problem Reporting

Incidents or events that meet the OHRP criteria for UPs require the creation and completion of an UP report form. The site investigator will report the UP to the IRB. The UP report will include the following information:

- Protocol identifying information: protocol title and number, PI's name, and the IRB project number;
- A detailed description of the event, incident, experience, or outcome;
- An explanation of the basis for determining that the event, incident, experience, or outcome represents an UP;
- A description of any changes to the protocol or other corrective actions that have been taken or are proposed in response to the UP.

To satisfy the requirement for prompt reporting, UPs will be reported using the following timeline:

- UPs that are SAEs will be reported to the IRB within a timeline that is in accordance with the policy
 of the investigator becoming aware of the event.
- Any other UP will be reported to the IRB within a timeline that is in accordance with the policy of the investigator becoming aware of the problem.
- All UPs should be reported to appropriate institutional officials (as required by an institution's
 written reporting procedures), the supporting agency head (or designee), and OHRP within a
 timeline that is in accordance with the policy of the IR's receipt of the report of the problem from
 the investigator.

9 Clinical Monitoring

Clinical site monitoring is conducted to ensure that the rights and well-being of human subjects are protected, that the reported trial data are accurate, complete, and verifiable, and that the conduct of the trial is in compliance with the currently approved protocol/amendment(s), with GCP, and with applicable regulatory requirement(s).

 Each clinical site will perform internal quality management of study conduct, data collection, documentation and completion. An individualized quality management plan will be developed to describe a site's quality management.

Version: 3.0

10 Statistical Considerations

10.1 Statistical Hypotheses

We hypothesize there will be a significant difference between the patient's experience in terms of comfort while being scanned using the attachment of the chin and forehead rest mounted on the existing ophthalmic devices. Additionally, we expect to see a significant improvement in time duration of adjusting motion artifacts.

10.2 Sample Size Determination

Let P1 be the proportion of patients who report improvement of comfort and then P0=1-P1 be the proportion of patients who report no difference between two devices. The primary outcome of interest is to see if P_1 is significantly bigger than 50% or not. With sample size of N=90 subjects, we will achieve 80% power to detect that P1 > 65.7% using a two-sided exact test of proportion with a significance level of 0.05. These results assume that the population proportion P1 under the null hypothesis is 50%.

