| Title | Comfortable and Stabilizing Chin & Forehead Rest Attachment for Slit Lamp Configurations |
|---|---|
| Short Title | Invention Study |
| Brief Summary | Cohort will consist of 150 subjects consisting of those that are healthy or have an existing eye disease. Subjects will be imaged on two OCT devices: device N, invention attached to the device and device C, the standard conventional device. The Imager will time multiple durations, one of them which will act to evaluate the number of motion artifacts that arise due to both the instability and lack of comfort the patient is experiencing in that particular moment. Following the imaging session, subject will be asked which device was more comfortable. |
| Phase | NA |
| Objectives | The primary objective is to ascertain that the OCT Imaging device with the invention attached provides a more comfortable experience for the subject. While the secondary objective is to reduce the time it takes for the system to account for the number of motion artifacts. |
| Methodology | Randomized |
| Study Duration | Until target number of subjects is reached |
| Participant Duration | One clinic visit |
| Duration of IP administration | One clinic visit |
| Study Sites | NYU Department of Ophthalmology |
| Number of participants | 150 subjects |
| Description of Study Agent/Procedure | Comfortable chin and forehead rest that can be adjusted to fit each individual's size. |
| Statistical Analysis | Descriptive statistics for continuous variables and categorical data, presented using frequency counts and percentages will be used for group and device comparison. Patient experience will be assessed using two-sided exact test of proportion. Comfort levels of each device will be compared using t test. Linear mixed effect models will be utilized to compare the time duration while accounting for inter-eyes correlations. |

Version: 3.0

Schematic of Study Design

Screening Period

- Total n=150
- · Obtain informed consent
- Screen potential subjects by inclusion and exclusion criteria
- Obtain history, document

Day of Imaging

1. Randomize Order of Devices

 Provide clinic with 150 envelopes in which they are assigned with instructions regarding which device and eye the Imager should begin with (C/N & OS/OD)

2. Study Intervention

- Measure the length of the subject's face
- Provide subject with questionnaire containing the following
 - o Are you feeling well?
 - o Are you feeling tired today?
 - o Are you uncomfortable?

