2.3 Rationale

This study primarily focuses on increasing the comfort for each patient's experience as well as reducing motion artifacts by improving the former, as well as stabilizing the patient's head, accomplished by adjusting the chin and forehead rest for each individual patient. The cohort will consist of a total of 90 subjects consisting of subjects that are both healthy and have an existing eye disease, as commonly observed in ophthalmology outpatient offices.

In order for certain limitations to not affect the validity of the results, various aspects of the trial will be randomized. This includes, but is not limited to, the order in which a patient will begin being imaged on either device C/N and which eye, OS/OD the Imager will scan first. This can help account for parameters including whether the time it takes to image the patient and/or level of comfort is affected as a result of their degree of alertness, energy level, how they are feeling on that particular day, etc.

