4.2.2 Secondary Study Endpoints

A secondary objective includes evaluating various time durations while a patient is being imaged to determine whether the amount of motion artifacts are in fact being reduced by implementing the invention to existing devices. In one of the standard clinical OCT imaging devices, the Cirrus OCT, there is an eye tracking mode that can be activated whilst imaging a patient. This feature selects a specific location within the eye and will constantly adjust, i.e. track, for the fine fixation adjustments that occur when a patient's eye is moving very slightly. Therefore, in order to view whether there are a higher number of motion artifacts found in one image versus another, the Imager can time the duration it takes from the moment that they click "acquire", to when the progress bar is full. This is because the more time it takes for the system to fully acquire an image it directly correlates to how still the subject's eye is. Additionally, the data acquisition time can also be affected by whether the Imager is able to acquire a clear fundus photo, i.e. when there are no media opacities as well as if the Imager properly corrects for the refractive error.

5 Study Enrollment and Withdrawal

We aim to enroll 150 total subjects including healthy volunteers and subjects that have an existing eye disease including, but not limited to, glaucoma, AMD, DR, and CSCR. The site can actively enroll new subjects and these subjects will be are continuously followed in their institute. The total NYU cohort will include 150 healthy subjects as well as any eye related disease suspect subjects. There will be no enrollment restrictions based on gender, ethnic origin or HIV status and the study population will reflect the demographics of NYU Department of Ophthalmology. Subjects from clinical groups will participate in all applicable sub-studies of the protocol.

Subjects will be included in both groups, labelled as either Group 1 (Novel) or Group 2 (Conventional). Both groups will include subjects that are identified with glaucoma, age related macular degeneration, diabetic retinopathy, and central serous chorioretinopathy or any other eye related disease as well as healthy volunteers that are recruited from the clinic that undergo the clinical examination as part of their routine clinical management and healthy volunteers that are invited to the clinic to undergo the clinical examination for the purpose of the study.

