5.6 Total Number of Participants and Sites

Recruitment will end when approximately 150 participants are enrolled at NYUMC.

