6.1.5 Administration

The order in which a subject will be imaged on either OCT imaging device C/N and whether the Imager will begin with either the OD/OS eye will be randomized. This will be done by providing the NYU Ophthalmology Clinic with a total of 90 envelopes that the Imager will choose from a mixed pile in which they will be evenly divided with a message to begin with device C/N and to begin with eye OD/OS.

The Standard Operating Procedure as to how to operate the novel device for imaging a subject can be seen below:

Version: 3.0

- 1. Sanitize chin and forehead rest
- 2. Seat subject by device
- 3. Move chinrest to either OD/OS
 - a. Slide chinrest to either right/left side
- 4. Size chinrest
 - a. Subject should place their chin in the rest and technician should either pull apart/push together the chin rest to either make it larger/smaller to fit the patient
- 5. Size mount of chinrest
 - a. Pull apart the mount easily to allow for the chinrest's length to be extended
- 6. Lock extension
 - a. Rotate knobs on both sides
- 7. Find correct/comfortable angular position of the chinrest
 - a. Push/move chinrest to position that it is comfortable i.e. not protruding into subject's neck and subject feels relaxed
- 8. Lock rotation
 - a. Tighten the bolt placed around the ball joint
- 9. Subject should rest forehead against the rest
- 10. Technician /imager should check if subject has to be adjusted closer to the device (based on the image from the device)
 - a. push/pull forehead rest by side of device so it will be adjusted along the grooved slot
- 11. Size forehead rest
 - a. tighten/loosen the strap on the side of the forehead rest to either make it smaller/larger for the patient (it will automatically lock into place)
- 12. Check if subject is comfortable, adjust if need be
- 13. Image subject according to scan protocol

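### Sample size and envelope count are each given as both 90 and 150, and the only power statement (for 90) pairs 65.7% with 80% power when the exact test gives about 85%

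*Combined protocol and SAP*

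**What the plan says.** **Number of participants**

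- Protocol Summary: "Cohort will consist of 150 subjects". The Schematic repeats 150 as the total.
- Section 5: "We aim to enroll 150 total subjects including healthy volunteers and subjects that have an existing eye disease". The same section then says: "The total NYU cohort will include 150 healthy subjects as well as any eye related disease suspect subjects".
- Section 5.6: "Recruitment will end when approximately 150 participants are enrolled at NYUMC".
- Section 2.3: "The cohort will consist of a total of 90 subjects".
- Section 10.2: "With sample size of N=90 subjects, we will achieve 80% power to detect that P1 > 65.7% using a two-sided exact test of proportion". The significance level is 0.05 and the null proportion is 50%.

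**Number of randomisation envelopes**

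- Schematic: "Provide clinic with 150 envelopes in which they are assigned with instructions".
- Section 6.1.5: "a total of 90 envelopes that the Imager will choose from a mixed pile".

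Section 10.3 confirms that the primary comfort question is analysed with the same two-sided exact test that Section 10.2 uses for power. The documents contain no allowance for dropout or unusable answers, and no sample size re-estimation that would turn 90 into 150.

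**The concern.** A sample size section should justify the number that will be recruited. Here it justifies 90, while the recruitment stop is about 150. A reader cannot tell what effect the trial is sized to detect, or why 60 more people are enrolled than the calculation used.

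Reading 90 as the evaluable number out of 150 enrolled does not work as the text stands. Section 2.3 gives 90 as the whole cohort, and Section 6.1.5 supplies 90 envelopes, which are used at randomisation and not at analysis.

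The second Section 5 statement can also be read as 150 healthy participants plus a further, unspecified number with eye disease.

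The envelope conflict could affect conduct. Section 2.3 relies on the randomised order of device and eye to protect the comparison from alertness, energy and similar effects. If 90 single-use envelopes are prepared and 150 people are enrolled, the last 60 have no randomised order.

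Section 10.2 states every input to its power figure, so the figure should reproduce. It does not.

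**Working it through.** **Inputs (all from Section 10.2):** N = 90, null proportion 0.50, P1 = 0.657, two-sided exact test of one proportion, alpha 0.05, stated power 80%.

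**Method.** Let X be the number who report improved comfort, X ~ Binomial(N, P1). The critical value c is the smallest integer with 2 × P(X ≥ c | N, 0.5) ≤ 0.05. The test rejects if X ≥ c or X ≤ N − c, so

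power = P(X ≥ c | N, P1) + P(X ≤ N − c | N, P1).

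**The plan's own figure, N = 90**

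- c = 54 gives a two-sided size of 0.0725, which is too large. c = 55 gives 0.0446. The rule is therefore to reject at ≥ 55 or ≤ 35.
- Power at P1 = 0.657 is 0.848. The stated figure is 80%, a difference of 4.8 percentage points.
- Power equals 80% at P1 = 0.648, which is 65.7 − 64.8 = 0.9 percentage points below the printed value.
- Power equals 85% at P1 = 0.6574, which rounds to the printed 65.7%.

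**Could another method give 80%?** At N = 90 and P1 = 0.657:

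| Method | Power |
|---|---|
| Normal approximation, two-sided 0.05 | 85.8% |
| Same, continuity-corrected | 83.2% |
| Wald | 88.1% |
| Wald, continuity-corrected | 85.7% |
| Arcsine | 85.8% |
| Exact, one-sided 0.05 | 89.3% |
| Exact, two-sided 0.025 | 72.3% |

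Two variants come close to 80%: a cut-off one step stricter than needed (≥ 56, size 0.026, power 79.1%), and 81 evaluable answers, that is a 10% loss from 90 (power 80.9%). The documents mention neither.

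**The same test at the enrolment target.** The row for 135 assumes that 10% of 150 give no usable answer (150 × 0.9 = 135). That rate is an illustration and is not in the documents.

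| Evaluable N | Reject at | Attained alpha | Power at 65.7% | P1 for 80% power |
|---|---|---|---|---|
| 90 | ≥ 55 or ≤ 35 | 0.045 | 84.8% | 64.8% |
| 135 | ≥ 80 or ≤ 55 | 0.039 | 95.1% | 62.4% |
| 150 | ≥ 88 or ≤ 62 | 0.041 | 97.0% | 61.7% |

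**Envelopes:** 150 − 90 = 60.

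**The case against.** The strongest reply has four parts.

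1. **The power sentence is safe.** Read as a floor, it is true: with 90 answers, any P1 above 65.7% has at least 84.8% power. Exact power is also saw-toothed, and 90 sits on a local peak. At 65.7%, power is 81.3% with 89 answers and 79.7% with 87, so 80% describes fairly what about 90 enrolled would deliver. This stands as a limit on the importance of the power error. It does not explain the printed figure, because Section 10.2 computes at N = 90 and states no loss. The match with 85% power is suggestive only; the documents do not show how 65.7% was obtained.

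2. **The envelope harm is conditional.** It arises only if Section 6.1.5 governs, 150 are enrolled, and envelopes are neither returned to the pile nor replenished. The section does not say. This stands, and the shortfall of 60 is a possible consequence of the conflict, not a documented one.

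3. **No section says which number governs.** This is true, and the sponsor must confirm it. The explicit recruitment stop in Section 5.6, supported by the Summary, the Schematic and Section 5, points to 150.

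4. **The 150-healthy wording in Section 5 is merely loose.** The opening of the same section and Section 5.6 make a total of 150 the natural reading. The statement still needs correcting, but it is a small part of the point.

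None of this reconciles 90 with 150 or supplies a power statement for 150.

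**Conclusion.** The point holds and should be fixed. The current text gives two participant totals and two envelope counts without explanation, and its only power statement does not cover the planned enrolment. This is the weightier part.

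The power mismatch is secondary. At N = 90, 65.7% carries 84.8% power where 80% is stated, an error of 0.9 percentage points in the detectable proportion, in the conservative direction. The primary test is not underpowered at 90 for 65.7%, and still less at 150.

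The figures assume that every counted participant gives one usable answer, that the null is 50%, and that the test is the two-sided exact test at 0.05, all as Section 10.2 sets out. The only outside assumption is the 10% loss behind the illustration at 135.

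**What to change.** On the basis that 150 is the intended total, which the sponsor should confirm:

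- **Section 10.2:** replace the power statement with wording such as: *With 150 participants giving an evaluable answer, the two-sided exact test (reject at ≥ 88 or ≤ 62 of 150, attained alpha 0.041) has 80% power at P1 = 61.7% and 97% power at 65.7%.* If a loss allowance is wanted, add: *With 135 evaluable answers (reject at ≥ 80 or ≤ 55, attained alpha 0.039) it has 80% power at 62.4% and 95% at 65.7%.* The sponsor should put its own loss rate behind any such sentence.
- **Sections 2.3 and 6.1.5:** change 90 to 150 for participants and envelopes, to agree with the Schematic and Section 5.6.
- **Section 5:** reword the cohort sentence as *150 subjects in total, healthy or with eye disease*.

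If 90 is in fact the required evaluable number, Section 10.2 should say so, pair 90 with 80% power at 64.8% (or about 85% at 65.7%), and justify the other 60 participants. The envelopes must still cover everyone enrolled.

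As an optional safeguard, separate from the error, the envelopes could be sealed, sequentially numbered and balanced over the starting device and eye. Exact balance over the four combinations is not possible with 150 (150 / 4 = 37.5), but 75 to 75 on device and on eye is.

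The cost is wording in four sections. There are no extra participants beyond the stated 150 and no change to the analysis method.
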